## 1.0 Objectives / Specific Aims

The specific aims of this protocol are to:

**Aim 1.** (Months 03-12). To theater test and deliver the un-adapted CPT protocol and one session adherence intervention (Lifesteps) with 12 trauma-exposed PLWH presenting for HIV treatment at the MUSC Ryan White Clinic and collect qualitative feedback for modifications to ensure feasible administration and relevant incorporation of HIV-related messages and/or content specific to HIV-related PTSD. Specific activities are to:

- A. Test methods and measurement protocol of the beta version of the research protocol.
- B. Utilize feedback provided through exit interviews, topical experts, and advisory panel discussion to shape any refinement of the integrated CPT and one session adherence protocol.
- C. Incorporate qualitative feedback into the CPT-L manual.

**Aim 2.** (Months 13-30). To assess feasibility of the modified CPT protocol (CPT-L) compared to Lifesteps in 60 PLWH with comorbid PTSD over 3 months (baseline, post intervention, 3 month follow-up) in a pilot RCT to assess key variables for subsequent efficacy testing (attendance, ART adherence, HIV symptom distress, CD4 count, viral load, PTSD symptoms, avoidant coping). Specific feasibility benchmarks are:

- A. Achieve a recruitment rate of 4+ patients per month and retention rate of 80% or higher.
- B. Obtain variability estimates of outcomes (less than 10% missing data) and initial indicators of treatment effects for the following hypotheses in the subsequent efficacy trial:
  - a. Participants who receive the CPT-L protocol will have improved HIV symptom distress, ART adherence, clinic attendance, and viral load at post intervention and 3-month follow up vs. control.
  - b. Participants who receive the CPT-L protocol will report lower PTSD at post intervention and 3-month follow up versus those in the Lifesteps Control.
- C. Assess qualitative feedback from exit interviews for high satisfaction, successful saturation of themes, and action plan development, in conjunction with Advisory Board, to refine the intervention for an R01.

**Exploratory Aims.** 1) We will assess between-group differences in other problems that commonly occur among PLWH and PTSD (substance misuse, depression). 2) Avoidant coping will be examined as a potential mechanism of action for the relationship between CPT-L and improved adherence.

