**Assessments and Data Collection Procedures.** The PC (blind to condition) will conduct the initial eligibility (baseline) diagnostic assessments and all study assessments. The CAPS will be audio-taped and study personnel will listen to a randomly selected 20% to ensure reliability of CAPS diagnosis over the course of the study. The PC will administer the battery in the HIV care clinic or remotely by phone to the participant, based on participant preference. All timepoints will be collected on all participants, even if they drop out of treatment. Pilot trials indicate that major assessments take between 1.5 – 2 hours to complete. Individuals will be given \$50 for completing the baseline interview, \$40 for attending the first session, then \$60 for post-intervention assessments and 20-minute exit interview after completion of CPT-L sessions (i.e., post intervention ~6 weeks after study enrollment); and a \$75 gift card for 3 month follow up surveys. Several questionnaires were drawn from the PROMIS common data elements and NIH sponsored repositories to promote data sharing (e.g., PROMIS depression and BRICS Social Determinants of Health). Participants will complete a brief electronic diary on a weekly basis to assess use of resources/additional supports. Research has demonstrated the validity of this approach, including capturing “real-time” data beyond what can be captured with retrospective reports. Surveys (<1 minute each) will be electronically collected once a week for the 6 weeks of the intervention period starting one week after randomization (i.e., 6 electronic survey entries), leading up to the 3-month follow up. With input from the CAB, we have established procedures to auto-send an email or SMS text (participant choice) on a set schedule. SMS text messaging is possible via Twilio, embedded within our REDCap system, which allows participants to complete a survey directly from their phone, without having to access a webpage. Participants will be asked permission for the study team to access electronic medical records to collect CD4 count and viral load at the time of enrollment. As an attending physician in the clinic, Co-I [name] is familiar with these electronic records and will oversee the data pull. CD4 T-cell counts and HIV viral load will be measured as standard clinical practice using standard clinical assays (HIV viral load less than 200 considered virologic suppression). Relevant data from the clinic’s electronic medical record (e.g., CD4 count, no-shows) will be collected at intervals and study completion (i.e., 6 months after participation) to document retention in HIV clinical care using the industry standard of 2 appointments with a provider with prescribing privileges per year, no longer than 6 months apart. PI [name] has planned for adequate staff training and coverage based on experience. The PI will assist in training research staff on consent, diagnostic interview, assessment measures, and medical chart data retrieval (with Co-I [name] and Co-I [name] for service utilization data) and will conduct weekly meetings, quarterly reviews, and booster trainings to ensure standardized procedures. See Table 2 for research instruments.

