## 12.0 Data Management

### Sample size, Statistical Power and Analysis

Sample size justification. As the study is designed to demonstrate feasibility, sample size was determined based on pragmatic considerations, rather than formal power analysis. The study plans to enroll 60 PLWH randomized to CPT-L or Lifesteps. This sample size is adequate to assess feasibility outcomes (enrollment, attrition, retention, adherence to protocol and fidelity). The sample size recruited during our recruitment period (18 months) will allow the team to specifically justify that we can approach a reasonable sample for a larger RCT in an expanded recruitment period. Further, with a target retention rate of ≥90%, an enrolled sample of 60 participants produces a 95% confidence interval from 82% to 98% and an adherence rate of 80% will produce a 95% confidence interval between 70% and 90%. The study will produce both within and between treatment group estimates of visit attendance (yes/no), ART adherence (85% of doses taken), and proportion of detectable viral load (yes/no). Further, if mean HIV Symptom Severity, CD4 cell counts, PCL and CAPS-5 scores will be assessed post-intervention and a sample of 30 participants in each group will provide adequate power to determine estimated a confidence interval with a difference of ½ a standard deviation (0.51 SD) of the between group mean estimate. If the difference in proportion of participants with detectable viral load is 10% in the CPT group and 20% in the SOC Lifesteps group at the close of treatment (10% difference), the sample of 30 participants in each study group will provide an 18% confidence interval on either side of the estimated difference.

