
Data Analysis Aim 2. Descriptive analyses will characterize the entire sample and two conditions as appropriate using measures of central tendency or frequency distributions and proportions. Feasibility will be determined by patient willingness to be screened, proportion of participants meeting PTSD criteria, and flow of participants through the study. Feasibility of assessments will be examined through self-report and medical record abstraction. While CPT has been evaluated in other populations, acceptability within PLWH is important for feasibility data. Intervention feasibility will be monitored through randomization, session attendance and quality assurance data collection on intervention fidelity and supervision. Exit interviews will be analyzed using the same techniques for qualitative analyses described for Aim 1. Study feasibility will be determined by ability to adequately randomize and retain study participants throughout study intervention and follow-up, determined through ability to successfully randomize 4+ patients per month and retain 90% of randomized patients throughout the study. In addition to retention, a low rate of missing primary outcome data ( $\leq 10\%$  missing) will demonstrate ability to integrate the intervention with standard clinical care components and medical health records. Protocol adherence will be monitored weekly and reported as the proportion of weekly PCL checklists completed, and distribution of clinician rated treatment engagement and cooperation levels. Acceptable protocol adherence will be determined by completion of  $\geq 80\%$  of assigned weekly PCL checklists across participants.

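### The Aim 2 retention benchmark is 80% in the Aims but 90% in the analysis plan, and nothing says which governs

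*Combined protocol and SAP*

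**What the plan says.** Section 1.0 (Objectives / Specific Aims) gives the first of its specific feasibility benchmarks for Aim 2 as: "Achieve a recruitment rate of 4+ patients per month and retention rate of 80% or higher".

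Section 12.0 (Sample size, Statistical Power and Analysis) returns to retention twice.

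- The sample size justification says that "with a target retention rate of ≥90%, an enrolled sample of 60 participants produces a 95% confidence interval from 82% to 98" per cent. The same sentence then says that "an adherence rate of 80% will produce a 95% confidence interval between 70% and 90" per cent. That second figure concerns adherence, not retention.
- The paragraph on data analysis for Aim 2 says: "Study feasibility will be determined by ability to adequately randomize and retain study participants throughout study intervention and follow-up". It makes this concrete as "determined through ability to successfully randomize 4+ patients per month and retain 90% of randomized patients throughout the study".

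Section 10.0 adds, on assessments: "All timepoints will be collected on all participants, even if they drop out of treatment".

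**The concern.** Section 1.0 and the Aim 2 analysis paragraph both pair retention with the same recruitment rate of at least 4 per month. They therefore describe the same feasibility test with two different pass marks. All of this is current text, and no sentence ranks the two values or presents them as a minimum and a goal.

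Feasibility is the main question of this pilot: Section 12.0 sizes the trial on practical grounds for that purpose, without a formal power calculation. Retention is one of the two quantities by which the analysis paragraph judges study feasibility. Section 13.0 also has the team follow retention and attrition while the trial runs. With two thresholds on paper and the running count visible, a result between them could be reported as met or not met according to which section is cited afterwards.

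**Working it through.** **Inputs.** 60 randomized in Aim 2 (Sections 6.0 and 12.0); retention thresholds of 80% (Section 1.0) and 90% (Section 12.0, twice); printed 95% interval of 82% to 98% (Section 12.0).

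**Step 1: reproduce the plan's interval.** Normal approximation, p ± 1.96 × √(p(1 − p)/n), n = 60.

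- p = 0.90: √(0.90 × 0.10/60) = 0.0387; half-width 1.96 × 0.0387 = 0.0759; interval 82.4% to 97.6%, which rounds to the printed 82% to 98%.
- p = 0.80: √(0.80 × 0.20/60) = 0.0516; half-width 0.1012; interval 69.9% to 90.1%, which matches the 70% to 90% printed for adherence.
- Neighbouring inputs do not round to the printed retention interval: p = 0.89 gives 81.1% to 96.9%, and p = 0.91 gives 83.8% to 98.2%.

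The 90% in the sample size paragraph is thus a worked input and not a misprint of 80%. The arithmetic there is correct.

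**Step 2: convert thresholds to counts.** 0.80 × 60 = 48 and 0.90 × 60 = 54. Counts from 48 (48/60 = 80.0%) to 53 (53/60 = 88.3%) satisfy Section 1.0 and fall short of the analysis paragraph.

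**Step 3: how often the two rules would disagree.** The documents give no expected retention apart from the two disputed values, so the true rates below are assumptions. With X binomial (n = 60, true rate p), the chance of disagreement is P(X ≥ 48) − P(X ≥ 54).

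| Assumed true retention | Meets 80% rule, P(X ≥ 48) | Meets 90% rule, P(X ≥ 54) | Rules disagree |
|---|---|---|---|
| 75% | 0.232 | 0.003 | 0.23 |
| 80% | 0.576 | 0.031 | 0.55 |
| 85% | 0.894 | 0.185 | 0.71 |
| 90% | 0.994 | 0.606 | 0.39 |
| 95% | >0.999 | 0.970 | 0.03 |

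**Step 4: could another 80% figure explain Section 1.0?** Section 12.0 has two others: the adherence rate in the precision statement, and completion of at least 80% of weekly PCL checklists as the mark of acceptable protocol adherence. Both are different measures, and neither turns the 80% retention benchmark into something else.

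**The case against.** The strongest reply is that little depends on the number. No go/no-go action is attached to either threshold, Section 13.0 states that there are no planned stopping rules, and data collection and participants are unaffected. If the retained count is reported with its interval, any reader can apply either mark. This stands, and it limits how serious the point is. It does not reconcile the sections.

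The probabilities are also only illustrative. They range from 0.03 to 0.71 with the assumed rate, and they treat participants as independent with one common rate across a 12-session arm and a one-session arm. The range of counts from 48 to 53 needs none of these assumptions, only that 60 are randomized.

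Three stronger readings are tempting, and the documents do not support them.

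- *The overall feasibility verdict flips between 48 and 53.* Other criteria apply: missing data, weekly PCL completion and qualitative feedback. If missing data were counted per participant at 3 months, which is an assumption, 48 to 53 retained would leave 12 to 7 of 60 missing (20.0% to 11.7%). The missing-data benchmark of about 10% would then fail under either retention threshold. If missingness is pooled over visits, or outcomes come from medical records, this need not follow.
- *Retention is undefined.* The analysis paragraph gives a denominator (those randomized) and a span (intervention and follow-up), and Section 1.0 gives a 3-month frame. Section 10.0 keeps assessing people who stop treatment, and Section 14.0 keeps withdrawn participants' data under intention to treat. Together these point to retention in assessment and not to completion of therapy. What is missing is the name of the qualifying assessment. Retention in HIV care, described in Section 10.0, is a separate outcome and not a competing definition.
- *The 18-month recruitment period contradicts the rate of 4 per month.* Sixty over 18 months averages 60/18 = 3.33 per month, but only if all 18 months are used. If 18 months is the time available, there is no conflict.

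**Conclusion.** The inconsistency is real and confined to one criterion. Section 1.0 sets retention at 80% or higher (48 of 60); the analysis paragraph sets 90% of those randomized (54 of 60), and the sample size paragraph agrees with 90%. For 48 to 53 retained, the plan gives two opposite answers on whether its retention criterion was met. At assumed true rates equal to the two stated values, that outcome has probability 0.55 (at 80%) and 0.39 (at 90%), rising to 0.71 at 85% between them.

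The documents do not settle which figure was intended. The point should be fixed because a pre-stated criterion ought to have one value and the repair is cheap. It does not call the design, the sample size or the efficacy analyses into question.

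**What to change.** Before outcome data are seen, state one retention threshold in Section 1.0 and in both paragraphs of Section 12.0, or say explicitly that one value is the minimum and the other the goal.

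- Keeping 90% changes only the threshold in Section 1.0. It is the harder benchmark: if true retention is exactly 90%, it is met about 61% of the time, against about 99% for the 80% criterion.
- Keeping 80% changes both paragraphs of Section 12.0, lowers the criterion now stated there, and makes the retention interval in the precision statement about 70% to 90%.

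In the same edit, name the qualifying assessment: for example, the 3-month assessment completed, among all randomized, whether or not treatment was completed.

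The cost is wording only, with no added participants, visits or recruitment time.

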## 2.0 Background

The prevalence of trauma exposure, and post-traumatic stress disorder (PTSD) in particular, among individuals living with HIV (30-74%) is higher than the general population (7-10%). Individuals with co-occurring PTSD and HIV are at high-risk for negative HIV-related outcomes, including low adherence to antiretroviral therapy (ART), faster disease progression, more hospitalizations, and almost twice the rate of death, as well as increased mental health problems. In addition to PTSD resulting from traumatic events, such as sexual and physical assault/abuse, negative reinforcement conceptual models suggest that the avoidant behavior (a hallmark symptom of PTSD) tied to HIV status-related PTSD can also contribute to poor ART adherence and to less success of viral suppression (e.g., by avoiding cues, such as ART medications, that serve as reminders of the HIV status). Despite the high rates of persons living with HIV/AIDS (PLWH) who report PTSD – and the poorer HIV patient outcomes among this population versus those without co-occurring PTSD – evaluation of the impact of evidence-based treatment for PTSD among populations living with HIV on HIV outcomes has been highly neglected in clinical research. In other words, no research to date has examined the critical question of whether HIV outcomes can be improved among the large number of PLWH with co-morbid PTSD and related consequences (e.g., substance misuse) by treating PTSD symptoms. To address this tremendous void in the field, we propose to adapt and examine the acceptability and feasibility of an evidence-based PTSD treatment that has reduced other HIV transmission behavior (e.g., sexual risk), Cognitive Processing Therapy (CPT), at an HIV clinic as a strategy to improve HIV outcomes in this population. We propose to do so in South Carolina (ranked 8th state in the country in 2019 for HIV/AIDS incidence; 11th for prevalence), where PLWH may also encounter additional HIV-related intersectional stigma, itself linked to increased avoidant coping and ART non-adherence.

The multi-disciplinary investigative team housed at the Medical University of South Carolina (MUSC) has leveraged: a) its long-standing relationship with the MUSC Ryan White clinic; b) pilot data collected by PI [name] [name]; c) consultant expertise in the HIV-PTSD link (Dr. [name]) and CPT (Dr. [name]); and d) an advisory panel made up of stakeholders and consumers (PLWH) to develop the proposed study, which aims to tailor CPT for PLWH with PTSD through integration of an adherence intervention, to demonstrate the acceptability and engagement of PLWH in CPT-L (CPT-Lifesteps), and to assess preliminary efficacy of CPT-L in improved adherence to ART, decreased viral loads, and retention in HIV care.

**PREMISE:** Although research has demonstrated a clear connection between PTSD and problematic HIV outcomes, the applicability, feasibility, and efficacy of evidence-based treatment for PTSD on HIV outcomes among people living with HIV (PLWH) has not been examined. Cognitive Processing Therapy (CPT) is an evidence-based PTSD treatment that effectively reduces avoidant coping, which similarly has been linked with ART non-adherence among PLWH. Thus, we will demonstrate how the proposed framework of an adapted CPT protocol (CPT-Lifesteps or CPT-L) offers great promise as an intervention to improve HIV outcomes related to quality of life, adherence, and subsequent viral suppression in PLWH by targeting PTSD and avoidant coping.

The proposed research plan is directly in line with several recently emphasized priorities of NIMH (*NOT-MH-20-013, Notice of Special Interest: Mental Health Comorbidities in HIV Prevention and Treatment*; and *PA-20-141: Formative and Pilot Intervention Research for Prevention and Treatment of HIV/AIDS*), the U=U campaign, and the national initiative Ending the HIV Epidemic (EHE) through targeting comorbid conditions.

PTSD is prevalent among PLWH and negatively impacts HIV outcomes. PLWH report higher levels of traumatic events (e.g., child maltreatment, sexual assault, physical assault) than the general population, with trauma exposure ranging from 40-90%. Higher rates of traumatic events/exposure correspond with higher rates of Posttraumatic Stress Disorder (PTSD) in this population, ranging between 30-74%. Beyond PTSD resulting from more conventional definitions of traumatic events (e.g., victimization, disasters), up to 64% of PLWH endorse PTSD symptoms directly related to HIV diagnosis or other issues related to the disease. PTSD is associated with other negative consequences, particularly substance use disorders (SUD) and depression. Lifetime prevalence of PTSD among people with SUDs is 50% compared to 7% in the general population, and comorbid PTSD and SUD display a worse course of illness, physical health and overall functioning, and increased risk of suicide than individuals with only PTSD or SUD. Addressing PTSD can significantly reduce SUD among various populations, although this has not been examined among PLWH.

The connection of PTSD (HIV- and non-HIV-related traumas) with problematic HIV outcomes has been well-documented. PLWH with PTSD have been shown to have faster HIV progression twice the rate of death, lower ART adherence, poorer retention in HIV care, and increased viral load compared to PLWH without co-occurring PTSD. Additionally, HIV-related stigma (community, anticipated, and internalized) is prevalent among PLWH and associated with problematic HIV outcomes (e.g., poor medication and visit adherence).

Trauma-focused treatment can be enhanced to address discrimination related to stigmatized identities (e.g., HIV-related intersectional stigma) associated with poorer outcomes in PTSD and ART adherence. HIV-related stigma is shame or disgrace affiliated with HIV and associated with negative health outcomes for PLWH. Fear of being judged by others predicted decreased ART adherence among PLWH and internalized HIV-stigma predicted poor ART adherence. Although individual treatment may not decrease society's harmful tendency to stigmatize PLWH [[and minoritized subgroups]], trauma-focused treatment may combat internalized stigma and misperceptions or over-anticipation of perceived stigma, thus preventing additional psychological distress and non-adherence linked with stigma.

Despite high rates of PLWH with co-occurring PTSD, the link between PTSD on HIV health related outcomes, and the negative reinforcement conceptual model (e.g., avoidant coping) that provides a theoretical framework for this link, research evaluating evidence-based PTSD treatment among seropositive populations on HIV outcomes is scarce. Gold standard, evidence-based treatments for PTSD, including Cognitive Processing Therapy (CPT), have strong evidence for reducing avoidance

symptoms, as well as traumatic stress, substance use, and depression among civilian and military adults with complex trauma histories. CPT reduces trauma-related self-blame and guilt, two factors intimately tied to avoidant coping. Most importantly, reductions in avoidance symptoms (in the context of traumatic stress symptoms) have been linked to increases in (non-HIV) medical regimen engagement, including medication adherence. Mental health treatment studies in adults with Type 2 diabetes (another chronic disease with self-management and adherence barriers) have demonstrated that interventions leading to mental health symptom reduction showed simultaneous improvements in medication adherence, HbA1C scores, and self-care behaviors. Although CPT has been enhanced to target alcohol use and high risk sexual behavior to prevent HIV among American Indian women, CPT, nor other gold-standard, empirically supported individual treatments (e.g., Prolonged Exposure/PE), have been adapted for PLWH or evaluated as an efficacious approach to reduce problematic HIV outcomes. Thus, there is critical need to examine evidence-based treatments for PTSD among PLWH and co-occurring PTSD to improve HIV outcomes. CPT may be particularly beneficial for PLWH due to the focus on unhelpful cognitions, or “stuck points,” in the form of assimilation (beliefs related to self-blame) and overaccommodation (extreme beliefs related to self and world). The flexibility of CPT to focus on unhelpful thoughts and thinking patterns would allow patients to address trauma- and HIV-related intersectional stigma cognitions in treatment. In line with the Undetectable=Untransmittable (U=U) initiative to end HIV-related stigma, this proposal has broad implications not only from a public health standpoint, but also for the self esteem of individuals by reducing HIV-related stigma [[and other intersecting stigmatized identities]]. Themes addressed in CPT (i.e., safety, intimacy, trust, esteem, power, and control), although originally created from theory on sexual assault, may have relevant overlap to unique issues in disclosing HIV status, and with managing and coping with HIV in interpersonal and intrapersonal domains. [[Given that 28-52% of PLWH are estimated to experience cognitive impairment (CI), CPT is particularly well-matched for application with this population, as CPT has been delivered successfully with veterans who have experienced traumatic brain injury (TBI), resulting in cognitive and affective symptoms similar to PLWH with CI.]] CPT dismantling studies have also demonstrated improved engagement and PTSD outcomes among complex and traditionally hard-to-reach populations, and can potentially decrease substance use in addition to PTSD symptoms, further supporting the intervention for complex mental health treatment needs of PLWH. Taken together, an empirically supported adaptation of CPT for PLWH (i.e., CPT-L) may improve HIV treatment outcomes for PLWH with comorbid PTSD. This study will address vital gaps by conducting the first pilot RCT to use an adapted evidence-based PTSD treatment, integrated with an evidence-based adherence session, (Lifesteps), to improve HIV outcomes among PLWH with co-occurring PTSD in a geographic jurisdiction identified in Phase 1 of the national End the Epidemic plan. To accomplish this goal, across 3 time-points, we will rigorously measure: trauma history, PTSD symptoms and diagnosis, viral load, CD4 count, stigma, ART adherence, clinic attendance, substance misuse, depression, and avoidant coping.
